### **Supportive Care**

While intrathecal rituximab has been well tolerated in all previously published reports, there are a number of potential toxic effects that will be anticipated. Since hypertension was the dose limiting toxicity in the phase 1 trial, specific aims will be outlined to manage changes in blood pressure around the time of rituximab administration.

Vital signs will be checked every 15 minutes for one hour after each intrathecal administration of rituximab (after one hour, vital signs will return to “routine” unless clinically warranted). For systolic blood pressure greater than 160 mmHg or diastolic blood pressure greater than 100 mmHg, labetalol 20 mg IV will be administered. An alternative agent will be prescribed if the patient’s heart rate is less than 70 beats per minute (e.g. hydralazine, enalaprilat). The management of hypertension can be further individualized if necessary at the discretion of the treating physician. For nausea or vomiting, ondansetron can be considered. If the patient is not over-sedated, a dopamine receptor blocking agent such as promethazine or prochlorperazine can be ordered. These agents will be available on an as needed basis only.

If a patient experiences any chest discomfort, a 12-lead electrocardiogram will be ordered.

For any shortness of breath, bronchodilators such as albuterol will be administered via nebulizer. Supplemental oxygen will be provided to maintain the oxygen saturation greater than 92%, and diagnostic imaging studies (e.g., chest x-ray or chest CT) will be ordered at the discretion of the treating physician or the PI of the study.

Any acute or subacute changes in mental status will warrant magnetic resonance imaging of the brain to rule out leukoencephalopathy.

### **Concomitant Medications/Therapy**

If warranted, patients will be able to commence treatment with systemic chemotherapy. If at all possible, high dose cytarabine and high dose methotrexate will be avoided while patients are undergoing intrathecal rituximab injections. However, this may not always be avoidable, and any patient that receives concomitant intrathecal rituximab and potentially neurotoxic systemic chemotherapy will be monitored closely for any toxicity that is out of the ordinarily expected effects from chemotherapy. If needed, whole brain or crano-spinal irradiation will be permitted during this study. Concomitant medications/therapy will be entered into the electronic case report form (PDMS/CORe).

### **Patient Evaluation**

#### **Pre-Treatment Evaluation**

- History and physical examination, including vital signs, height, weight and performance status.
- Blood will be drawn for routine tests.
- Diagnostic lumbar puncture
- Concomitant drugs and side effects will be evaluated and recorded.

#### During Treatment Evaluation

Twice weekly evaluations until two consecutive CSF samples are negative for the presence of blast cells. After the patient's CSF cytology is negative, patients will be evaluated weekly for one month, then every other week thereafter.

- Physical examination, including vital signs, weight and performance status.
- Blood will be drawn for routine tests.
- Concomitant drugs and side effects will be evaluated and recorded.

#### Follow-Up

- Serious adverse events will be captured until 30 days after the last dose of drug.

#### Long-term Follow-up

- Patients will be followed for survival every 6 to 12 months after completion of active treatment and while still on study or be enrolled on the leukemia department long-term follow-up umbrella protocol.

#### **Adverse Events**

We will use the CTCAE version 4 for toxicity and adverse event reporting. A copy of this can be found at: <http://ctep.info.nih.gov>

#### **Criteria for Response**

Patients will be considered as responding to therapy if the CSF is without evidence of blast cells after four lumbar punctures with rituximab. Clinical improvement and diagnostic imaging may also be used to support a patient's response to therapy.

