##### ***Diagnosis***

Diagnosis of CNS leukemia involves assessing the cerebrospinal fluid (CSF) by lumbar puncture (LP) or intraventricular sampling. Signs and symptoms include headache, mental status changes, motor deficits, and seizures. In most patients, the CSF is abnormal (protein concentration greater than 50 mg/dL, leukocyte count greater than 4 per mm^3, and positive cytology). A positive cytology by itself is diagnostic of LMD. In leukemias and lymphomas, the yield of positive cytology following one or two lumbar punctures is approximately 70% (3).

Neuroradiographic imaging can also be involved in the diagnostic workup, to include cranial computed tomography (CT), magnetic resonance imaging (MRI), CT-myelography, and radionuclide CSF flow studies (4). However, imaging studies have a high false negative rate.

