##### ***Treatment of Leptomeningeal Disease***

Treatment of LMD involves the entire neuroaxis, therefore treatment must be designed to encompass the entire subarachnoid space. Radiation therapy to the entire neuroaxis produces severe bone marrow suppression and has generally not been effective in controlling active CNS disease even in radiosensitive malignancies (4). Systemic chemotherapy for LMD is limited in its utility due to poor penetration of the blood brain barrier (with the exception of the administration of high dose methotrexate or cytarabine) and due to difficulties attaining prolonged intra-CSF drug exposure. Determining the response to therapy primarily involves the clearance of blasts from the CSF along with clinical improvement.

The incidence of CNS relapse with or without bone marrow recurrence in adults with ALL is approximately 7% (1). In this series, patients were treated with intensive chemotherapy and/or CNS prophylaxis with IT methotrexate and cytarabine. Despite a high response rate (clearing CNS disease), median survival for these patients was 6 months, and the 1-year survival rate was 28%.

In our institution, patients who are diagnosed with CNS leukemia are started on intrathecal chemotherapy on a twice weekly schedule of administration. This continues until two consecutive CSF samples are negative for the presence of blast cells. After the patient's CSF cytology is negative, patients commence on maintenance intrathecal chemotherapy weekly for one month, followed by one intrathecal injection with chemotherapy administration every other week thereafter. Methotrexate has been the most widely employed drug for intrathecal treatment of LMD. The terminal half-life of intrathecal methotrexate is 14 hours. The toxicities of intrathecal methotrexate can be exacerbated by the administration of concurrent systemic chemotherapy or radiation. Cytarabine is another active agent administered intrathecally in the treatment of LMD. Typically, these two agents are given on an alternating schedule to potentially minimize toxicity and maximize effectiveness.

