### **Inclusion Criteria**

Patients must have relapsed or refractory CD20+ lymphoid malignancies with either documented CNS involvement or peripheral nerve infiltration.

Patients 3 years of age and older are eligible after 3 patients (age 15 or older) have been treated and did not experience a dose limiting toxicity. Patient 3 to 15 years of age will follow the dose escalation schema independent of the adults.

ECOG performance status measure will be used. (ECOG Performance Status less than or equal to 3)

Adequate liver function (bilirubin less than or equal to 3 mg/dL within 24 hours of enrollment)

Adequate renal function (serum creatinine less than or equal to 3 mg/dL within 24 hours of enrollment)

Urine pregnancy test for women of childbearing potential (defined as *not* post-menopausal for 12 consecutive months or no previous surgical sterilizations). A negative urine pregnancy test is required within 48 hours of initiating study drug.

Signed informed consent

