#### **Criteria for Removal from Study**

Progressive or resistant disease (defined as CSF with persisting blasts after four intra-lumbar administrations of rituximab, which is after 2 weeks of therapy)

Unacceptable severe (grade 3-4) toxicity that is possibly related to the study drug and persists despite dose optimization and optimal management of toxicity.

Patient choice

Failure to comply with study schedule

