## Phase II

Phase II part is a single arm study using the dosage level recommended from phase I. The patients treated at the MTD in phase I will be included in phase II part, and the sample size for phase II can be up to 22. The trial will be continuously monitored for efficacy and toxicity (non-hematological  $\geq$ grade 3). The method of Thall, Simon, and Estey will be used to perform interim efficacy and safety monitoring (15).

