## **Efficacy**

The primary endpoint is the response defined as the CNS is without evidence of blast cells after four lumbar punctures with rituximab. The historical data suggested the response rate by chemotherapy (methotrexate and/or cytarabine) is about 10%. The targeted improved overall response rate is 25%, The trial will be continuously monitored. The study will be stopped early if the data suggest that:

$$\Pr(\pi > 0.1 | \text{data}) < 0.05$$

Here  $\pi$  is the response rate. That is, if at any time during the study we determine that there is a less than 5% chance that the response rate is greater than 10%, we will terminate the study. The response

rate is assumed to follow a non-informative prior of Beta (0.2, 1.8). The study will be stopped early if (The number of responders)/ (The number of patients evaluated)  $\leq 0/9$ .

Table 2: Operating characteristics for monitoring of overall response rate

| True Response Rate | Early Stopping Probability | Median Sample size (interquartile) |
|--------------------|----------------------------|------------------------------------|
| 0.05               | 0.63                       | 9 (9, 22)                          |
| 0.1                | 0.40                       | 22 (9,22)                          |
| 0.15               | 0.23                       | 22 (22,22)                         |
| 0.2                | 0.14                       | 22 (22,22)                         |
| 0.25               | 0.08                       | 22 (22,22)                         |

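### The response definition does not require CSF blasts before the first rituximab dose, so it is undefined how patients with nothing to clear count in the response rate and the 0/9 futility rule

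*Protocol*

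**What the plan says.** **Endpoint.** The Protocol's Criteria for Response read: "Patients will be considered as responding to therapy if the CSF is without evidence of blast cells after four lumbar punctures with rituximab". Its Efficacy section, repeated in the SAP, reads: "The primary endpoint is the response defined as the CNS is without evidence of blast cells after four lumbar punctures with rituximab". Both look only at the state after four rituximab lumbar punctures (LPs).

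**Who can enter.** The Inclusion Criteria accept "CD20+ lymphoid malignancies with either documented CNS involvement or peripheral nerve infiltration". A positive CSF sample is not a condition. Selection of Patients also admits patients given intrathecal methotrexate or cytarabine at the first LP, at least 48 hours before rituximab. The Pre-Treatment Evaluation lists a diagnostic LP, with no required result and no repeat after such chemotherapy.

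**Who is counted.** The Analysis method section puts everyone with at least one dose into the efficacy analysis. The futility rule in Efficacy stops the trial at 0/9 for the ratio "The number of responders)/ (The number of patients evaluated" (outer brackets omitted), and its denominator is not defined. For phase II, "the sample size for phase II can be up to 22".

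**What points to clearance as the intended endpoint.** The background on leptomeningeal disease says: "Determining the response to therapy primarily involves the clearance of blasts from the CSF along with clinical improvement". Criteria for Removal from Study refer to "CSF with persisting blasts after four intra-lumbar administrations of rituximab". The twice-weekly phase in Selection of Patients and the During Treatment Evaluation both run until two consecutive samples are free of blasts.

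**What partly covers two groups.** Statistical Considerations say that nerve-only patients have no well-defined response metric, that their clinical and radiologic response will be recorded, and that so few are expected that the analysis is unaffected. Selection of Patients analyses those with and without earlier intrathecal chemotherapy separately.

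**The concern.** A patient whose CSF holds no blasts at the first rituximab dose, and still holds none after four LPs, meets the written endpoint without any drug effect. The plan leaves room for such patients: CNS disease documented other than by cytology (the Diagnosis section allows imaging in the workup), CSF already cleared by methotrexate or cytarabine, and peripheral nerve disease only.

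Two results depend on how these patients are counted. One is the primary response rate, read against a historical 10% and a target of 25%. The other is the futility rule, which within 22 patients can fire only while there are no responders at all. One patient scored as a responder without having had blasts would switch it off. If such patients instead stay in the all-treated denominator as non-responders, the rate is diluted and an active drug is slightly more likely to be stopped. The text does not choose between these.

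**Working it through.** **Inputs from the Protocol.** Prior Beta(0.2, 1.8); stop if Pr(π > 0.1 | data) < 0.05; boundary 0/9; historical rate 10%; target 25% (all from Efficacy). Phase II maximum 22 (Phase II).

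**Step 1: reproduce the plan's rule.** After x responders in n patients the posterior is Beta(0.2 + x, 1.8 + n − x).

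| x/n | Pr(π > 0.1) |
|---|---|
| 0/8 | 0.053 (continue) |
| 0/9 | 0.045 (stop) |
| 1/9 | 0.436 |
| 1/22 | 0.124 |
| 1/31 | 0.0506 |
| 1/32 | 0.0457 |

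The 0/9 boundary is reproduced. With one responder the rule would first fire at 32 patients, beyond the maximum of 22. So P(stop) = (1 − p)^9, which gives 0.630, 0.387, 0.232, 0.134 and 0.075 at true rates of 5, 10, 15, 20 and 25%. Table 2 gives 0.63, 0.40, 0.23, 0.14 and 0.08. The rule and its table are sound; the gap is in who counts.

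**Step 2: add baseline-negative patients.** Assumptions: k of 22 patients have no CSF blasts before the first dose, they arrive in random order, each is scored a responder with probability r, and p is the true rate in baseline-positive patients.

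- P(at least one in the first nine) = 1 − C(22−k, 9)/C(22, 9) = 0.41, 0.66, 0.81 for k = 1, 2, 3.
- P(stop) = Σ_j Hypergeom(j; 22, k, 9) × (1 − r)^j × (1 − p)^(9−j).
- Apparent rate at 22 patients = [k r + (22 − k) p]/22.

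Example with k = 1. The chance that the patient is outside the first nine is 13/22 = 0.591.

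- Scored as a responder (r = 1), p = 0.10: P(stop) = 0.591 × 0.387 = 0.229; apparent rate (1 + 2.1)/22 = 14.1%.
- Kept as a non-responder (r = 0), p = 0.25: P(stop) = 0.591 × 0.0751 + 0.409 × 0.1001 = 0.085; apparent rate 5.25/22 = 23.9%.

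| Scoring and quantity | k = 0 | k = 1 | k = 2 | k = 3 |
|---|---|---|---|---|
| All responders: P(stop), true 5% | 0.63 | 0.37 | 0.21 | 0.12 |
| All responders: P(stop), true 10% | 0.39 | 0.23 | 0.13 | 0.07 |
| All responders: true 10% appears as | 10% | 14.1% | 18.2% | 22.3% |
| Half responders: P(stop), true 10% | 0.39 | 0.32 | 0.26 | 0.21 |
| Half responders: true 10% appears as | 10% | 11.8% | 13.6% | 15.5% |
| All non-responders: P(stop), true 10% | 0.387 | 0.405 | 0.423 | 0.443 |
| All non-responders: P(stop), true 25% | 0.075 | 0.085 | 0.097 | 0.110 |
| All non-responders: true 25% appears as | 25% | 23.9% | 22.7% | 21.6% |

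The effect is larger when these patients are scored as responders than when they are not.

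**The case against.** The strongest reply is that the plan plainly means clearance. The background section, the treatment schedule, the evaluation schedule and the removal criterion all presuppose blasts to clear, and CNS involvement must be documented. Investigators may well score only patients who started positive. This stands as evidence of intent. But none of these passages is the endpoint definition, and none says who enters the overall rate or the 0/9 denominator.

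Two of the three groups are partly handled. Statistical Considerations suggest that the CSF test is not meant for nerve-only patients, and pretreated patients are to be analysed separately. Both points stand. However, the first does not say that nerve-only patients leave the denominator, and the all-treated efficacy set says otherwise. The second does not extend to the 0/9 rule, which is stated once for all patients.

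Much of the rule's fragility is by design: at a true 10%, a genuine responder appears among the first nine with probability 1 − 0.387 = 0.61, which also ends any chance of stopping. The gap would add to this for a reason unrelated to drug activity.

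Three stronger readings are tempting, and the documents do not support them:

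- **That the response rate is necessarily biased upward.** This holds only if baseline-negative patients are scored as responders. Keeping them as non-responders is also compatible with the text, and then the bias is downward.
- **That about 30% of patients will be blast-free.** The Diagnosis section says "the yield of positive cytology following one or two lumbar punctures is approximately 70" per cent, but this describes the diagnostic yield in leukemias and lymphomas, not the share of enrolled patients with positive CSF.
- **That the change from CSF to CNS between the two definitions is a second endpoint.** Both tie the finding to lumbar punctures, so CSF is evidently meant. It is a wording matter.

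**Conclusion.** The concern holds as a gap in the definition of the primary endpoint and of the futility denominator. It should be fixed, with medium confidence that it matters in practice. Read literally, the text scores a patient with nothing to clear as a responder, and the passages that imply otherwise do not govern the overall rate or the 0/9 rule.

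The size is conditional. It rests on an assumed 1 to 3 baseline-negative patients among 22, arriving in random order, and on how they are scored. Under the most unfavourable scoring, three such patients take a true 10% to an apparent 22.3%, close to the 25% target, and cut the chance of futility stopping from 0.39 to 0.07. Under the opposite scoring they raise the chance of wrongly stopping at a true 25% by up to 3.5 percentage points (0.075 to 0.110). With none, nothing changes. The plan's statement that the analysis will not be affected is therefore secure only if no such patients enrol or a rule says how they are counted.

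**What to change.** 1. In Criteria for Response and in both Efficacy sections, define response as clearance of CSF blasts that were present in the last sample before the first rituximab dose. For patients given earlier intrathecal methotrexate or cytarabine, that sample is the CSF drawn at the first rituximab LP before instillation. Use the term CSF throughout.
2. State that the patients evaluated in the 0/9 rule are these baseline-positive patients.
3. Report the response rate in this set alongside the all-treated rate from Analysis method, and name which is primary. Either choice is workable. Making the baseline-positive set primary is a design change that the sponsor should make openly; keeping the all-treated set primary is the smaller amendment.
4. Report baseline-negative and nerve-only patients separately, keep them in the safety analysis, and replace the statement in Statistical Considerations that the analysis will not be affected with this rule.

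**Cost.** A Protocol and SAP amendment, and cytology on CSF from an LP that is already being done. The response denominator shrinks, and patients with a false-negative baseline sample drop out of that set. The ninth evaluable patient comes a little later: on average 9 × 23/(23 − k), that is the 9.4th, 9.9th or 10.4th treated for k = 1, 2, 3. As a stress case only, if 70% of patients were evaluable, about 22 × 0.7 = 15.4 would be, the ninth would be about the 9/0.7 = 12.9th treated, and the chance of fewer than nine among 22 would be about 0.001. The futility rule would still operate.

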### **Background Drug Information:**

#### ***Systemic Rituximab***

Rituximab is a chimeric monoclonal antibody directed at the CD20 antigen. It was initially approved for systemic use in 1997 to treat non-Hodgkin's lymphoma (6). Subsequent to the drug's approval, it has been studied in a number of different oncologic situations, including chronic lymphocytic leukemia (CLL), acute lymphoblastic leukemia (ALL), and as part of the mobilization program for hematopoietic stem cell transplantation. Recently, the addition of rituximab to chemotherapy has been shown to improve overall survival (OS) in younger patients with CD20 positive ALL (5). Moreover, in CLL, rituximab

combined with fludarabine and cyclophosphamide has also improved the outcome of patients compared to conventional chemotherapy programs (7).

The major toxicities of systemically administered rituximab are primarily related to the infusion of the drug, and may include fever, chills, rigors, rash, headache, and hypotension (6). These reactions are potentially fatal, and are typically seen during the first infusion. Most infusion reactions can be ameliorated by administering the drug slowly, and escalating the infusion rate only as the patient tolerates. Premedications are also vital, and might include histamine blocking agents, acetaminophen, and/or corticosteroids. Other potential toxicities include tumor lysis syndrome and mucocutaneous eruptions. Rarely, reactivation of JC virus leads to progressive multifocal leukoencephalopathy.

Penetration of rituximab across the blood brain barrier is a problem due to the drug's large molecular size. Investigators have conducted pharmacokinetic analyses showing that CSF levels of rituximab are 0.1 – 4% of the concomitant serum concentration (8, 9). Rituximab, while highly effective as a systemic therapy, does not reduce the risk of lymphoma recurrence in the central nervous system (10).

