### **Statistical Considerations**

The primary outcome of the study will be response rate. Time to recurrence of CNS leukemia and overall survival will be secondary outcomes. Time to recurrence and survival will be considered from the date of CNS relapse diagnosis.

There is no well-defined metric to measure response to treatment in patients with peripheral nerve involvement only. Clinical and radiologic response will be recorded and it is expected that few to no patients with only peripheral nerve involvement will actually be involved and therefore the statistical analysis will not be affected.

A maximum of 25 patients will be enrolled in this phase I/II study, with about 12 patients/year.

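### Response is defined as CSF without blast cells, but any CD20+ lymphoid malignancy is eligible, so read literally, persistent CLL or mature lymphoma cells in the CSF can be scored as a response

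*Protocol*

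**What the plan says.** **Who is eligible.** Protocol, Inclusion Criteria: "Patients must have relapsed or refractory CD20+ lymphoid malignancies with either documented CNS involvement or peripheral nerve infiltration". The title, the objective and Selection of Patients are equally broad, and no section limits enrollment by histology. The background discusses non-Hodgkin's lymphoma and CLL as well as ALL. The phase I study from which the 25 mg level is taken was in CNS and intraocular lymphoma.

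**How response is defined.** Under Criteria for Response, the protocol counts a patient as a responder when "the CSF is without evidence of blast cells after four lumbar punctures with rituximab". Protocol, Efficacy, repeated in the SAP under the same heading: "The primary endpoint is the response defined as the CNS is without evidence of blast cells after four lumbar punctures with rituximab". The two sentences differ in naming the CSF and the CNS, but both rest on blast cells.

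**Related criteria.** Criteria for Removal from Study defines resistant disease by blasts that persist after four administrations. Statistical Considerations, in both documents, states: "Time to recurrence of CNS leukemia and overall survival will be secondary outcomes".

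Neither document defines blast cells to include lymphoma or CLL cells, and neither gives a criterion by histology. Statistical Considerations admits a gap in measuring response only for patients with peripheral nerve involvement alone.

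**The concern.** In ordinary hematological usage the malignant cells of CLL and of mature B-cell lymphomas are not blasts. The protocol's own background keeps the terms apart: it speaks of blast cells when describing CNS disease in leukemia, and of positive cytology when describing diagnosis in leukemias and lymphomas together. A patient can therefore enter on positive cytology and be scored on a narrower finding.

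If the CSF of such a patient contains malignant cells but no blasts both before and after four doses, the endpoint as written is met and the resistance criterion is not. A later CNS recurrence of lymphoma would also fall outside the secondary outcome. Both errors favor the drug. Phase II is a single-arm comparison of at most 22 patients, with a historical rate of 10% and a target of 25%, and its only efficacy stop requires no responders among the first nine, so a small number of false responses matters.

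**Working it through.** **1. Reproduce the plan's rule.** Inputs from Efficacy: prior Beta(0.2, 1.8); stop if Pr(π > 0.1 | data) < 0.05; boundary 0/9. The phase II maximum of 22 is from Phase II. After x responses in n patients the posterior is Beta(0.2 + x, 1.8 + n − x).

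- 0/8: Pr(π > 0.1) = 0.053, continue.
- 0/9: Pr(π > 0.1) = 0.045, stop. This matches the stated boundary.
- 1/22: Pr(π > 0.1) = 0.124, so a single responder keeps the trial open to the end.

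Stopping therefore happens only if the first nine patients yield no response, with probability (1 − p)^9 at true rate p. For p = 0.05, 0.10, 0.15, 0.20 and 0.25 this gives 0.630, 0.387, 0.232, 0.134 and 0.075. Table 2 states 0.63, 0.40, 0.23, 0.14 and 0.08. The agreement is within 2 percentage points, and no figure in the plan is disputed.

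**2. Add misscoring.** Let f be the share of patients whose malignant cells are not blasts, and m the share of their true non-responses scored as responses. With the same true rate p in both groups, the recorded rate is

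q = p + (1 − p) × f × m,

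and the stopping probability is (1 − q)^9. The documents give neither f nor m; both are assumptions and are varied here. The chance of at least one such patient among the first nine is 1 − (1 − f)^9.

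True rate p = 0.05:

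| f | m | Recorded rate q | Early stopping (1 − q)^9 | At least one such patient in first nine |
|---|---|---|---|---|
| 0 | – | 0.05 | 0.63 | – |
| 5% | 1 | 0.05 + 0.95 × 0.05 = 0.0975 | 0.40 | 37% |
| 10% | 1 | 0.05 + 0.95 × 0.10 = 0.145 | 0.24 | 61% |
| 20% | 1 | 0.05 + 0.95 × 0.20 = 0.24 | 0.08 | 87% |
| 30% | 1 | 0.05 + 0.95 × 0.30 = 0.335 | 0.03 | 96% |
| 20% | 0.5 | 0.05 + 0.95 × 0.10 = 0.145 | 0.24 | 87% |
| 20% | 0.25 | 0.05 + 0.95 × 0.05 = 0.0975 | 0.40 | 87% |

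At the historical rate, p = 0.10, with f = 20% and m = 0.5: q = 0.10 + 0.90 × 0.10 = 0.19, and early stopping falls from 0.39 to 0.15.

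The rows with m = 1 are the most that the wording can do at each share. The last two rows show how quickly the effect shrinks if assessors mostly read the endpoint as negative cytology.

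**The case against.** The strongest reply is that blasts is shorthand. Treatment of Leptomeningeal Disease and During Treatment Evaluation both describe samples free of blasts and then, in the next sentence, call the same state negative cytology. Diagnosis makes positive cytology sufficient for leptomeningeal disease. The literal reading also has an odd result under Selection of Patients: a patient with no blasts at baseline would count as negative from the start. All this points to loose terminology, and an assessor may well score a report of lymphoma cells as not cleared. That stands as evidence of intent. It does not settle the endpoint, because those sections describe institutional practice and the visit schedule, and the endpoint sentences carry no such equivalence.

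Three further points stand in part:

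- The setting is a leukemia department (collaborators, long-term follow-up, adverse event guidelines), so the share of mature B-cell disease may be small. Eligibility does not make it zero.
- Some lymphomas have blast morphology and would be covered. The accurate statement is that such patients can be scored as responders, not that every lymphoma patient will be.
- Any single response, true or false, disables the 0/9 rule. That sensitivity belongs to the rule; the wording adds one avoidable route to it.

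Clinical improvement and imaging may support a response under Criteria for Response, but they do not replace the CSF test.

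**Conclusion.** The point holds as a mismatch between the eligible population and the written endpoint. Followed exactly, the response rule can count persistent disease as cleared, and the secondary outcome omits CNS recurrence of lymphoma. The direction is towards apparent efficacy. The size is unknown: it depends on an undocumented case mix and on how assessors read the term. The figures for complete misscoring are upper bounds for each assumed share.

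A reader might infer from the 20% row (recorded rate 24%) that an inactive drug would reach the 25% target. The documents do not support that. It needs an assumed share and the misscoring of every such patient at once, and the two sections that equate absence of blasts with negative cytology make complete misscoring the extreme case. The reason to correct the wording does not depend on that scenario.

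**What to change.** - **Response** (Protocol, Criteria for Response and Efficacy; SAP, Efficacy): define it as CSF cytology negative for malignant lymphoid cells (blasts, lymphoma cells or CLL cells) after four lumbar punctures with rituximab. Name the CSF in all three places, since Efficacy in both documents now says CNS.
- **Secondary outcome** (Statistical Considerations, both documents): recurrence of CNS disease instead of CNS leukemia.
- **Reconcile**: Selection of Patients, During Treatment Evaluation and Criteria for Removal from Study use the same blast wording to drive the schedule and removal. They must be reconciled with the revised term. How the clinical rules should then read is for the investigators.

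**Cost.** The same CSF samples and cytology reports serve. The prior, the 0/9 boundary and Table 2 do not change. The downside is that the observed response rate may be less favorable than under the literal wording. Because the term also appears in the schedule and removal sections, the amendment reaches beyond the statistical text.
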